## **5.5 CRITERIA FOR TEMPORARILY DELAYING**

During a regional or national emergency declared by a governmental agency, if the site is unable to adequately follow protocol mandated procedures, contingency measures proposed in [Section 10.9](#) (Appendix 9) should be considered.

## 6 STUDY INTERVENTION(S) AND CONCOMITANT THERAPY

Study intervention is defined as any investigational intervention, marketed product and placebo intended to be administered to a study participant according to the study protocol.

The study interventions, Amcenenstrant/Amcenenstrant-matching placebo and Tamoxifen/Tamoxifen-matching placebo, will be administered as a flat-fixed dose, and not by body weight or body surface area.

### 6.1 STUDY INTERVENTION(S) ADMINISTERED

**Table 3 - Study intervention(s) administered**

Intervention label	Amcenenstrant 200 mg (SAR439859)	Amcenenstrant matching placebo	Tamoxifen 20 mg	Tamoxifen matching placebo
Intervention name	Amcenenstrant 200 mg (SAR439859)	Amcenenstrant matching placebo	Tamoxifen 20 mg	Tamoxifen matching placebo
Intervention description	QD-tablet	QD-tablet	QD-tablet	QD-tablet
Type	Drug	Drug	Drug	Drug
Dose formulation	Tablet	Tablet	Tablet	Tablet
Unit dose strength(s)				
Dosage level(s)	1 tablet once a day with food, at approximately the same time every day (±3 hours)	1 tablet once a day with food, at approximately the same time every day (±3 hours)	1 tablet once a day with food, at approximately the same time every day (±3 hours)	1 tablet once a day with food, at approximately the same time every day (±3 hours)
Route of administration	Oral	Oral	Oral	Oral
Use	Experimental active	Experimental placebo	Comparator	Comparator placebo
IMP and NIMP	IMP	IMP	IMP	IMP
Packaging and labeling	Amcenenstrant 200 mg will be provided in child resistant bottles (32 tablets per bottle). Labelling will be as required per country requirement	Amcenenstrant matching placebo will be provided in child resistant bottles (32 tablets per bottle). Labelling will be as required per country requirement	Tamoxifen 20 mg will be provided in child resistant wallets (32 tablets per wallet). Labelling will be as required per country requirement	Tamoxifen matching placebo will be provided in child resistant wallets (32 tablets per wallet). Labelling will be as required per country requirement
[Current/former name(s) or alias(es)]	Amcenenstrant 200 mg (SAR439859)	Amcenenstrant matching placebo	Tamoxifen 20 mg	Tamoxifen matching placebo

**Table 4 - Study arm(s)**

Arm title	A	B
Arm type	Experimental	Active comparator
Arm description	Amcenestrant (SAR439859) 200 mg + Tamoxifen Placebo	Amcenestrant Placebo + Tamoxifen 20 mg
Associated intervention labels	None	None

### 6.1.1 Treatment starts after randomization

All participants entered into the study will be treated within 3 working days of randomization. A participant may receive additional study interventions if he/she meets retreatment criteria as determined by the Investigator and agrees to be retreated. Throughout the study, study intervention will be blinded.

### 6.1.2 Patient diaries

Participants will receive study drug diaries for Amcenestrant/Amcenestrant-matching placebo and Tamoxifen/Tamoxifen-matching placebo to document study intervention intake, and the completed study drug diaries should be returned to the study site at the subsequent study visit.

### 6.1.3 Drug dispensation

IMPs are dispensed at each protocol-scheduled on-site visit as defined in the SoA ([Section 1.3](#) “IMP dispensation call” row). Between the protocol-scheduled on-site visits, interim visits may be required for IMP dispensing. As an alternative to these visits, IMPs may be supplied from the PI/site to the participant via a Sponsor-approved courier company where it was allowed by local regulations and agreed up on by the participant.

For a regional or national emergency declared by a governmental agency that results in travel restrictions, confinement, or restricted site access, contingency measures are included in [Section 10.9](#) (Appendix 9): Contingency measures for a regional or national emergency that is declared by a governmental agency.

### 6.1.4 Amcenestrant/Amcenestrant-matching placebo

Amcenestrant/Amcenestrant-matching placebo will be administered orally at a dose of 200 mg once daily in fed condition and at approximately the same time each day ( $\pm 3$  hours), together with Tamoxifen/Tamoxifen-matching placebo. The daily dose of amcenestrant (SAR439859) tablets is to be swallowed whole with water. The two tablets should be taken within 5 minutes. Study participants should be instructed not to bite or chew on the tablets.

### **6.1.5 Tamoxifen/Tamoxifen-matching placebo**

Tamoxifen/Tamoxifen-matching placebo will be administered orally at a dose of 20 mg once daily and at approximately the same time each day ( $\pm 3$  hours), together with Amcenenestrant/Amcenenestrant-matching placebo. The two tablets should be taken within 5 minutes. Study participants should be instructed not to bite or chew on the tablets.

Refer to the Tamoxifen Summary of Product Characteristics for additional administration instructions.

### **6.1.6 Non-investigational medicinal products**

Goserelin or other GnRH analog, approved for use in early breast cancer as per site/country availability, will be administered in male participants without prior orchiectomy and in pre/perimenopausal women.

Refer to the corresponding Summary of Product Characteristics for additional administration instructions.

## **6.2 PREPARATION, HANDLING, STORAGE, AND ACCOUNTABILITY**

The Investigator or designee must confirm appropriate temperature conditions have been maintained during transit for all study interventions received and any discrepancies are reported and resolved before use of the study intervention.

Only participants enrolled in the study may receive study intervention and only authorized site staff may supply or administer study intervention. All study intervention must be stored in a secure, environmentally controlled, and monitored (manual or automated) area in accordance with the labeled storage conditions with access limited to the Investigator and authorized site staff. The investigator, institution, or the head of the medical institution is responsible for study intervention accountability, reconciliation, and record maintenance (ie, receipt, reconciliation, and final disposition records).

Partially used and used study intervention will be destroyed at the study site according to the standard practices of the site after an accurate accountability has been performed and signed by the Investigator (or the pharmacist). A detailed treatment log form of the destroyed study intervention will be established with the Investigator (or the pharmacist) and countersigned by the Investigator and the Monitoring Team.

The Investigator must not destroy the unused IMP unless Sanofi provides written authorization. Further guidance and information for the final disposition of used and unused study medications are provided in the pharmacy manual and/or monitoring plan.

Any quality issue noticed with the receipt or use of an IMP (deficiency in condition, appearance, pertaining documentation, labeling, expiration date, etc) must be promptly notified to the Sponsor. Some deficiencies may be recorded through a complaint procedure (see [Section 8.3.7](#)).

A potential defect in the quality of IMP may be subject to initiation of a recall procedure by the Sponsor. In this case, the Investigator will be responsible for promptly addressing any request made by the Sponsor, in order to recall the IMP and eliminate potential hazards.

Under no circumstances will the Investigator supply IMP to a third party, allow the IMP to be used other than as directed by this clinical trial protocol, or dispose of IMP in any other manner.

### **6.3 MEASURES TO MINIMIZE BIAS: RANDOMIZATION AND BLINDING**

Two systems requiring log in by the investigator will be used:

- Medidata Rave EDC system, to be used to complete the eCRF
- The IRT system for registration, randomization and drug supply information

Both systems are accessible 24 hours a day, 7 days a week.

The log in instructions for Rave EDC system and IRT system will be provided to each investigator prior to site authorization.

Screening and randomization will be performed in three steps:

- **Step 1: Screening**

Participants will be recorded directly in the IRT system. At this stage, date of signature of informed consent and questions related to stratification factors (see [Section 4.1](#)) should be completed. Patient identifier will be created. In parallel, tumor sample has to be sent for central pathology assessment to confirm ER and PgR status.

- **Step 2: Eligibility criteria data collection and central confirmation of ER and PgR biomarkers**

Once a patient is registered in the IRT system, the investigator should log in on the Medidata Rave EDC system, to complete the eligibility related baseline information.

Note that the tumor material shipment and imaging work up can be performed while patient is still treated with AI. The other assessments/questionnaires required before randomization should be performed/completed when the participant is off the prior AI therapy.

- **Step 3: Randomization**

Once eligibility criteria, ER / PgR status and discontinuation of prior AI therapy due to treatment-related toxicity have been confirmed, the participant could be randomized in the IRT system. During this step, stratification factors should be confirmed in the IRT system.

- The randomized intervention kit number list is generated centrally by Sanofi.
- The IMPs are packaged in accordance with this list.

- The randomization and intervention allocation are performed centrally by an IRT. The IRT generates the participant randomization list and allocates the intervention number and the corresponding intervention kits to the participants according to it. Details of the IRT procedure will be provided in the IRT Site Manual.
- Participant cannot be randomized more than once in the study.
- Warning: the randomization will not be possible if study treatment and ER/PgR central results are not available at site. Please consider adequate timeframe.

### **Methods of blinding**

- As per the double blind and double-dummy design, all randomized patients will also receive the matching-placebo corresponding to the other treatment arm. Amcnestrant-matching placebo will be supplied as tablets identical to amcnestrant 200 mg tablets in appearance. Tamoxifen-matching placebo will be supplied as tablets identical to tamoxifen 20 mg tablets in appearance. IMPs (amcnestrant, tamoxifen) and their matching-placebo will be supplied in indistinguishable boxes
- The EORTC and the SANOFI study teams will be blinded to treatment allocation until the database lock for the primary analysis of the primary endpoint IBCFS. An independent unblinded statistician will be appointed by the EORTC HQ in order to prepare confidential reports for the IDMC reviews. Other intermediate reports (safety reports, data surveillance report, newsletters) issued before the primary analysis of IBCFS endpoint will be prepared by the blinded study teams. Medical review will be conducted blinded to treatment allocation.

### **Unblinding**

The investigator and the site staff may be unblinded in one of the following cases:

- Emergency unblinding: In case of emergency, the investigator has the sole responsibility to decide if unblinding of the participant's treatment allocation is warranted. The Investigator should make every effort to contact the Sponsor and/or Sponsor's representatives prior to unblinding a participant's intervention assignment unless this could delay emergency treatment of the participant. The unblinding requests should be made by the investigator through the IRT system. The date and reason that the blind was broken must be recorded in the source documentation and case report form, as applicable. If the code is broken, the participant must withdraw from the IMP administration.
- Unblinding after the first IBCFS event: Blinding codes may also be broken after a patient discontinues treatment due to disease recurrence, as determined by the treating investigator, but only if deemed essential to allow the investigator to select the patient's next treatment regimen and after discussion and agreement with the Sponsor.
- Code should not be broken in the absence of emergency situations or disease recurrence.
- The blinded EORTC statistician and the Sponsor's statistician will receive the treatment allocations after the database lock for the primary analysis of the primary endpoint IBCFS.
- Sponsor's safety team may unblind the treatment allocation assignment for any participant with an SAE.

## 6.4 STUDY INTERVENTION COMPLIANCE

Administration of the IMP will be supervised by the Investigator or Sub-investigator.

IMP accountability:

Intervention units are returned by the participant at each visit. In case of DTP process, the intervention units can be returned by the carrier (if defined in the contract).

The Investigator counts the number of tablets, remaining in the returned packs, and fills in the Intervention Log Form.

The Investigator records the dosing information on the appropriate page(s) of the CRF.

The monitor in charge of the study then checks the CRF data by comparing them with the IMP which he/she has retrieved and intervention log forms.

At each dispensation visit, when participants are dispensed with study intervention at the site, they will receive study intervention directly from the Investigator or designee, under medical supervision. On days when there are no on-site visits, study participants will take the study intervention at home. The study staff will demonstrate to the patient how to record information on study intervention intake in study medication diary. Study participants will have to complete the study medication diary and the completed study medication diary should be returned to study site at subsequent site visit. In case of an early vomiting event, the administered dose of study intervention should not be repeated.

When participants take study intervention at home, compliance with study intervention will be assessed at each visit, using study medication diaries and study medical record (study source documentation). Compliance will be assessed by direct questioning, counting returned tablets during the site visits and documented in the source documents and CRF. Deviation(s) from the prescribed dosage regimen should be recorded in the eCRF.

A record of the number of amcnestrant/amcnestrant-matching placebo, tamoxifen/tamoxifen-matching placebo tablets and goserelin or other GnRH analog, dispensed to and taken by each participant must be maintained and reconciled with study intervention and compliance records. Intervention start and stop dates, including dates for IMP omissions and NIMP delays/omissions will also be recorded in the CRF.

## 6.5 DOSE MODIFICATION

No dose reduction of study intervention is permitted. Dose adjustment in case of treatment-related toxicity is managed by dose omission.

Dose adjustment guidelines for study intervention (amcnestrant/amcnestrant-matching placebo and tamoxifen/tamoxifen-placebo) in case of treatment-related toxicity could be found in [Section 10.10.1](#) (Appendix 10).

### 6.5.1 Missed doses

- Any doses of study intervention that are not taken within 6 hours of the intended time should be considered as missed dose.
- If the participant misses a dose of study intervention, a double dose should not be taken the next day to compensate the missed dose.
- If the participant vomits a dose of study intervention, an additional dose should not be taken, and this information must be recorded in the study medication diary. The next prescribed dose should be taken at the usual time.
- Doses omitted for toxicity are not to be replaced within the same cycle.

### 6.5.2 Retreatment criteria in case of treatment-related toxicity

Study treatment may be held up to 28 days to permit sufficient time for recovery from the toxicity. For patients not recovering from toxicity within 28 days, a delay >28 days is permitted if the patient benefits from the study intervention; the investigator will contact the Sponsor or Sponsor's representatives for the retreatment. In absence of clinical benefit, permanent discontinuation of the study intervention should be considered.

### 6.5.3 Restarting study medications following treatment interruption

The criteria for restarting study medication following an interruption that was unrelated to toxicity from study intervention, examples including:

- For a regional or national emergency declared by a governmental agency, contingency measures are included in [Section 10.9](#) (Appendix 9): Contingency measures for a regional or national emergency that is declared by a governmental agency.
- Patients with diagnosis of second non-breast primary invasive cancers may be considered for temporary discontinuation (treatment temporarily suspended to allow for local treatment of the second non-breast primary cancer).
  - If the interruption does not exceed 3 months in any 12-month time period with systemic therapy not required and no evidence of breast cancer recurrence, study treatment can be re-started.
  - If the interruption >3 months and the patient benefits from the study intervention, the investigator will contact the Sponsor or Sponsor's representatives for the retreatment. In absence of clinical benefit, permanent discontinuation of the study intervention should be considered.
- If Sponsor or Sponsor-representative's approval to restart/rechallenge participant with study intervention is not granted, then participant must permanently discontinue study intervention and may continue in the study for protocol-specified follow up assessments.

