### **2.2.7 Rationale for the primary endpoint**

IDFS as per STEEP criteria, defined as the time from the date of randomization to the date of the first event of ipsilateral invasive breast tumor recurrence, regional invasive recurrence, distant recurrence, death, contralateral invasive breast cancer, or second non-breast primary invasive cancer, has been widely used as primary endpoint in recent adjuvant breast cancer studies

[monarchE (50), PALLAS (51), EarLEE-2 (52). However, the inclusion of the event of second primary cancer in the IDFS definition was a subject of considerable discussion:

- As noted in Hudis et al, (4) it may be difficult to distinguish a second primary cancer in a nonbreast site (which may or may not be related to the primary cancer) from a distant recurrence of the primary breast cancer especially when the tumor site is not easily accessible for biopsy.
- There is a well-known association between treatment and some second primary cancers. This is the case, for instance, of tamoxifen-induced endometrial cancer. Including events not related to the primary breast cancer or to the administered treatment might eventually dilute the treatment effect. Thus, including most types of second primaries of non-breast origin, except endometrial cancer, may be less relevant to the assessment of the treatment benefit of amcnestrant over tamoxifen in terms of improving breast cancer outcomes.
- In addition, it has been shown in independent cohorts that the rate of second primary invasive cancers of nonbreast origin is increasing with age (53, 54). Considering that recent clinical trials enrolled older patients, the risk of second primary invasive cancers that might not be related to the primary breast cancer or to the treatment of the study population is not negligible.

Based on these considerations, we have opted for IBCFS as the primary endpoint, excluding the second non-breast primary invasive cancers as event of interest. Our primary endpoint selection was also based:

- on the use of IBCFS as the primary endpoint in other Phase 3 trials conducted in patients diagnosed with HER2-positive early breast cancer (54, 55).

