Potential risk of clinical significance	Summary of data/rationale for risk	Mitigation strategy
Other: Study intervention Tamoxifen		
Uterine malignancies	An increased incidence of uterine malignancies (endometrial adenocarcinoma and uterine sarcoma), including fatal cases, has been reported with tamoxifen treatment.	
Promptly evaluate abnormal vaginal bleeding in woman with current or past tamoxifen use.
 
Patients receiving or who have previously received tamoxifen should have annual gynecological examinations. Advise patients to promptly inform healthcare providers if they experience any abnormal gynecological symptoms (eg, menstrual irregularities, abnormal vaginal bleeding, changes in vaginal discharge, or pelvic pain or pressure).

Thromboembolic events	There is an increased incidence of thromboembolic events, including DVT and pulmonary embolism, during tamoxifen therapy.	
Carefully consider the risks and benefits of tamoxifen in women with a history of thromboembolic events.
 
Advise patients to seek medical attention immediately if signs or symptoms of a thromboembolic event occur.
 
Participants with abnormal coagulation profiles, or any history of coagulopathy within 6 months prior to the first dose of IMP including history of DVT or pulmonary embolism should be excluded (exclusion criterion: E 07).

Hepatotoxicity	
Tamoxifen has been associated with changes in liver enzyme levels, and on rare occasions, a spectrum of more severe liver abnormalities including fatty liver, cholestasis, hepatitis, and hepatic necrosis. Some of these serious cases included fatalities. In most reported cases, the relationship to tamoxifen is uncertain. However, some positive rechallenges and dechallenges have been reported.
 
Liver cancer and liver abnormalities, some fatal, have occurred.
	Perform periodic liver function testing as indicated in the protocol (as mentioned above for amcenestrant).

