#### **8.3.1 Time period and frequency for collecting AE and SAE information**

All AEs and SAEs will be collected from the signing of the ICF at the time points specified in the SoA ([Section 1.3](#)) and until at least 30 days after administration of the last study intervention. After this period, all ongoing related AEs, all ongoing SAEs regardless of relationship with study treatment, and all new related AEs (serious or nonserious), are to be reported and followed up until resolution or stabilization. All SAEs and AESI will be recorded and reported to the Sponsor or Sponsor's representatives immediately and under no circumstance should this exceed 24 hours, as indicated in Appendix 3 ([Section 10.3](#)). The Investigator will submit any updated SAE data to the Sponsor within 24 hours of it being available.

Investigators are not obligated to actively seek AE or SAE after conclusion of the study participation. However, if the Investigator learns of any SAE, including a death, at any time after a participant has been discharged from the study, and he/she considers the event to be reasonably related to the study intervention or study participation, the Investigator must promptly notify the Sponsor.

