**e) Is a congenital anomaly/birth defect**

**f) Other situations:**

- Medical or scientific judgment should be exercised by the Investigator in deciding whether SAE reporting is appropriate in other situations such as significant medical events that may jeopardize the participant or may require medical or surgical intervention to prevent one of the other outcomes listed in the above definition. These events should usually be considered serious.
- Note: The following list of medically important events is intended to serve as a guideline for determining which condition has to be considered as a medically important event. The list is not intended to be exhaustive:
  - Intensive treatment in an emergency room or at home for:
    - Allergic bronchospasm
    - Blood dyscrasias (ie, agranulocytosis, aplastic anemia, bone marrow aplasia, myelodysplasia, pancytopenia, etc)
    - Convulsions (seizures, epilepsy, epileptic fit, absence, etc).
  - Development of drug dependence or drug abuse
  - Suicide attempt or any event suggestive of suicidality
  - Syncope, loss of consciousness (except if documented as a consequence of blood sampling)
  - Bullous cutaneous eruptions
  - Cancers diagnosed during the study or aggravated during the study

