### Assessment of causality

- The Investigator is obligated to assess the relationship between study intervention and each occurrence of each AE/SAE.
- A "reasonable possibility" of a relationship conveys that there are facts, evidence, and/or arguments to suggest a causal relationship, rather than that a relationship cannot be ruled out.
- The Investigator will use clinical judgment to determine the relationship.
- Alternative causes, such as underlying disease(s), concomitant therapy, and other risk factors, as well as the temporal relationship of the event to study intervention administration will be considered and investigated.
- The Investigator will also consult the Investigator's Brochure (IB) and/or Product Information, for marketed products, in his/her assessment.
- For each AE/SAE, the Investigator **must** document in the medical notes that he/she has reviewed the AE/SAE and has provided an assessment of causality.
- There may be situations in which an SAE has occurred and the Investigator has minimal information to include in the initial report to Sponsor. However, **it is very important that the Investigator always make an assessment of causality for every event before the initial transmission of the SAE data to Sponsor.**
- The Investigator may change his/her opinion of causality in light of follow-up information and send an SAE follow-up report with the updated causality assessment.
- The causality assessment is one of the criteria used when determining regulatory reporting requirements.

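### Section 6.5.3 classes every second non-breast primary as unrelated to study-drug toxicity and lets blinded treatment restart within 3 months without sponsor contact, although Section 2.2.7 and Table 1 tie uterine malignancy to tamoxifen

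*Combined protocol and SAP*

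**What the plan says.** Section 6.5.3 opens by limiting its scope: "The criteria for restarting study medication following an interruption that was unrelated to toxicity from study intervention, examples including". One of its examples is a second non-breast primary invasive cancer for which study treatment is suspended to allow local treatment. No tumor site is set apart. For a pause of up to 3 months in any 12-month period, "with systemic therapy not required and no evidence of breast cancer recurrence, study treatment can be re-started". For a longer pause, the investigator must contact the Sponsor about retreatment. The last bullet says that a participant stops permanently if sponsor approval to restart is refused.

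Sections 1.1 and 4.1 leave continuation to the treating physician, on condition that it is in the patient's best interest. They cap the suspension at the same 3 months. Section 7.1.1 ties sponsor approval to interruptions beyond 3 months.

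On the drug risk, Section 2.2.7 discusses second primaries that are associated with treatment: "This is the case, for instance, of tamoxifen-induced endometrial cancer". Table 1 states: "An increased incidence of uterine malignancies (endometrial adenocarcinoma and uterine sarcoma), including fatal cases, has been reported with tamoxifen treatment". The mitigation listed there is prompt evaluation of bleeding, annual gynecological examination and advice to report symptoms. Section 8.2.1 schedules the examinations.

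**The concern.** The protocol names uterine cancer as a tamoxifen risk and looks for it every year, but does not say what happens to study drug when it is found. The only rule that fits the event by name, the second-primary bullet in Section 6.5.3, sits under a lead-in that assumes the interruption is not drug toxicity. For most second primaries that assumption is reasonable. For endometrial adenocarcinoma and uterine sarcoma it does not fit the protocol's own risk table.

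The stake is patient safety. A participant who has just had local treatment for a uterine cancer, and who has an even chance by allocation of having been assigned tamoxifen, could be put back on the same blinded treatment without anyone beyond the site having been asked first.

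**Working it through.** The plan states no figure on this point, so the check is a comparison of passages.

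**1. Which rule applies to a uterine cancer needing local treatment only?**
- If the investigator does not attribute it to study drug: Section 6.5.3. Restart is allowed up to 3 months, and sponsor contact is required only beyond that.
- If the investigator does attribute it: Section 6.5.2 and Table 14. The duty to judge is clear: "The Investigator is obligated to assess the relationship between study intervention and each occurrence of each AE/SAE". Treatment may be held for 28 days, and beyond that "For patients not recovering from toxicity within 28 days, a delay >28 days is permitted if the patient benefits from the study intervention", with sponsor contact. Table 14, which is headed as recommendations, lets the same dose resume after an attributed Grade 3 or first Grade 4 event has resolved to Grade 1 or less, or to Grade 2 or less if that is not a safety risk.
- Neither route has a rule for uterine malignancy. A pause of 29 to about 91 days (3 months) calls for sponsor contact on the second route and not on the first. This shows that the classification matters; it does not measure harm.

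**2. Does any other passage require review before restart?**

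| Safeguard | Section | What it does | Review required before a restart within 3 months? |
|---|---|---|---|
| Physician judgement, best-interest condition | 1.1, 4.1 | Makes restart discretionary | No |
| Stop for any AE that the investigator thinks warrants it | 7.1.1 | Allows a stop | No |
| Cancer listed as medically important: "Cancers diagnosed during the study or aggravated during the study" | 10.3.2 | Points to SAE status | No |
| SAEs "reported to the Sponsor or Sponsor's representatives immediately and under no circumstance should this exceed 24 hours" | 8.3.1 | Informs the Sponsor | No |
| Safety team may unblind for an SAE | 6.3 | Optional | No |
| Permanent stop if approval to restart is refused | 6.5.3, last bullet | Gives effect to a refusal | Not clearly: it does not say that approval must be sought for a short pause |

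**3. Does the protocol write mandatory stops elsewhere?** Yes: for pregnancy (Section 8.3.5) and for a Grade 4 ALT increase (Table 14). A specific rule would therefore be in keeping with its style.

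**4. Size.** The documents give no incidence of uterine cancer, no share treated locally, no restart rate and no risk on re-exposure. For scale only, every rate below is an assumption. The 1869 per arm includes men, so the counts are upper bounds at these rates.
- Uterine cancer on tamoxifen, 0.3% to 1.0%: 1869 × 0.003 = 5.6; 1869 × 0.010 = 18.7.
- Local treatment only, 50% to 80%: 5.6 × 0.5 = 2.8; 18.7 × 0.8 = 15.0.
- Actually restarted, 5% to 50%: 2.8 × 0.05 = 0.1; 15.0 × 0.5 = 7.5.
- Amcenestrant at 0.1% to 0.3%, same local share: 1869 × 0.001 × 0.5 = 0.9; 1869 × 0.003 × 0.8 = 4.5.
- Both arms reached by the fix: 2.8 + 0.9 = 3.7 to 15.0 + 4.5, about 19.4 from unrounded values. Of 3738, that is 0.1% to 0.5%.

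The range for actual re-exposure starts at practically nobody. The textual gap does not depend on any of these rates.

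**The case against.** The strongest reply is that the protocol already leaves several people able to prevent an unwise restart. Restart is permitted, never ordered. In a double-dummy trial the investigator knows that the participant may be on tamoxifen, and nothing in the documents suggests that blinding makes a physician less careful. A uterine cancer attributed to study drug falls outside Section 6.5.3 by its own lead-in. The final bullet of that section is not nested under the longer interruption, so it can be read as giving the Sponsor a veto over any restart. Section 6.1.5 refers sites to the tamoxifen Summary of Product Characteristics, and Section 10.3.3 has the investigator consult the product information when judging causality. A restriction after uterine cancer may stand in the label, which is not available here.

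Most of this stands, and it limits the point. A reader might infer that the Sponsor is kept out of the matter, or that the protocol directs re-exposure. The documents support neither. A reader might also set exclusion E 04, which asks for at least 5 years free from another solid tumor, against the 3-month restart. E 04 is an entry rule for solid tumors and lymphoma in general, and it admits a past uterine cancer once that time has passed, so it is not evidence of a re-exposure standard.

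What the reply does not remove is that the second-primary bullet covers these cancers without distinction under a label that Table 1 contradicts for uterine malignancy. No listed safeguard clearly has to operate before treatment resumes.

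**Conclusion.** The point holds as an internal mismatch with a safety consequence. Section 6.5.3, with Sections 1.1 and 4.1, treats a named tamoxifen risk as unrelated to study-drug toxicity and allows a discretionary restart within 3 months without a required review.

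Two stronger conclusions are tempting and not supported. One is that a material number of participants would be harmed: the documents link tamoxifen to the occurrence of uterine cancer but say nothing on re-exposure after local treatment, and the counts above rest on assumed rates. The other is that no effective safeguard exists: several do, and they make the residual gap narrow.

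The number affected is probably small and cannot be quantified from the documents. There is no effect on type I error, power or the planned 568 events. The conclusion rests on reading the last bullet of Section 6.5.3 together with Section 7.1.1, that is, as applying where approval has to be sought. On the broader reading the gap shrinks further, and the wording is still worth settling. This is a clarification to consider, not a defect that blocks the trial.

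**What to change.** In the second-primary bullet of Section 6.5.3, and in the matching text of Sections 1.1 and 4.1, add for both arms: after a uterine malignancy (endometrial adenocarcinoma or uterine sarcoma), blinded study treatment is stopped. It is not restarted, whatever the length of the interruption, unless the investigator has contacted the Sponsor and obtained approval. Follow-up for all endpoints continues. Cross-reference the rule in Section 7.1.1 and Table 14. Leave the exception in Section 6.8 as it is, so that local surgery or radiotherapy remains allowed.

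The review should be done blinded, treating the participant as possibly on tamoxifen. Section 6.3 already keeps medical review blinded. A decision taken after unblinding by the safety team could reveal the arm to the site and would need an exception to the stop-on-unblinding rule in Section 7.1.1. A blinded decision avoids both.

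The cost is a few sentences in the next amendment and a note to sites. A few participants, including some on amcenestrant, may stop treatment early. They stay in the ITT analysis under the treatment policy strategy of Table 8, so the primary analysis and sample size do not change.
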